6.4.3 Exploratory Efficacy Endpoints

The exploratory efficacy endpoints are as follows:

- Incidence of asthma exacerbations *from baseline through Week 54*, with asthma exacerbation defined as in [Appendix 12](#)
- Incidence of severe asthma exacerbations *from baseline through Week 54*, with *severe asthma exacerbation* defined as asthma symptoms requiring hospitalization or resulting in death attributed to asthma
- *Incidence of asthma exacerbations from baseline through Week 70*
- Relative change in pre-bronchodilator FEV₁ (liters) *from baseline to Week 54*
- Absolute change in pre-bronchodilator FEV₁ (percentage predicted) *from baseline to Week 54*
- Absolute change from the randomization visit in pre-bronchodilator FEV₁ (liters) at Week 70
- *Achievement of improvement in SGRQ score, defined as a decrease of ≥ 4 points from baseline to Week 54*
- *Achievement of improvement in ACQ-7 score, defined as a decrease of ≥ 0.5 points from baseline to Week 54*
- Clinician's global impression of change patient's asthma symptoms, as assessed through use of the CGIC, *from baseline to Week 26 and Week 54*
- Incidence of asthma exacerbations *from baseline through Week 54* within each of the eosinophil-high (≥ 300 cells/ μ L) and eosinophil-low (< 300 cells/ μ L) groups
- Absolute change *from baseline to Week 54* in pre-bronchodilator FEV₁ (liters) within each of the eosinophil-high (≥ 300 cells/ μ L) and eosinophil-low (< 300 cells/ μ L) groups
- Incidence of asthma exacerbations *from baseline through Week 54* by *IL1RL1* genotype
- Absolute change in pre-bronchodilator FEV₁ (liters) *from baseline to Week 54* by *IL1RL1* genotype

Analysis of exploratory efficacy endpoints will be described in the SAP.

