1. BACKGROUND

The purpose of this document is to provide details of the planned analyses for Study GB39242. The primary focus of this Statistical Analysis Plan (SAP) is on analyses of complete data from the first 54 weeks of the study, which includes the 2-week single-blind placebo run-in as well as the 52-week double-blind treatment period. Such analyses are described in the main body of this document and will be performed after all patients have completed 54 weeks in the study or discontinued early, and all corresponding data have been entered into the database, reviewed, and verified. The 16-week follow-up period of the study may be ongoing at the time of the 54-week analysis. No changes to the SAP will be allowed at the time of or subsequent to the 54-week primary analysis.

The analyses specified in this document supersede the high-level analysis plan described in the protocol.

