2.1 OUTCOME MEASURES

2.1.1 Primary Efficacy Endpoint

The primary efficacy endpoint is as follows:

- Incidence of asthma exacerbations from baseline through Week 54, with asthma exacerbation defined as new or increased asthma symptoms (wheezing, coughing, dyspnea, chest tightness, and/or nighttime awakenings due to these symptoms) that result in one or both of the following:
 - Hospitalization or an emergency department visit with administration of systemic corticosteroids treatment
 - Treatment of systemic corticosteroids for ≥ 3 days or a long-acting depot corticosteroid preparation with a therapeutic effectiveness of ≥ 3 days

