2.1.3 Exploratory Efficacy Endpoints

The exploratory efficacy endpoints are as follows:

- Incidence of asthma exacerbations from baseline through Week 54, with asthma exacerbation defined as in [Appendix 5](#)
- Incidence of severe asthma exacerbations from baseline through Week 54, with severe asthma exacerbation defined as asthma symptoms requiring hospitalization or resulting in death attributed to asthma
- Incidence of asthma exacerbations from randomization visit through Week 70
- Relative change in pre-bronchodilator FEV₁ (liters) from baseline to Week 54
- Absolute change in pre-bronchodilator FEV₁ (percentage predicted) from baseline to Week 54
- Absolute change in pre-bronchodilator FEV₁ (liters) from baseline to Week 70
- Achievement of improvement in St. George's Respiratory Questionnaire (SGRQ) score, defined as a decrease of ≥ 4 points from baseline to Week 54
- Achievement of improvement in ACQ-7 score, defined as a decrease of ≥ 0.5 points from baseline to Week 54
- Clinician's global impression of change (CGIC) in patient's asthma symptoms, as assessed through use of the CGIC, from baseline to Week 26 and Week 54
- Incidence of asthma exacerbations from baseline through Week 54 within each of the eosinophil-high (≥ 300 cells/ μ L) and eosinophil-low (< 300 cells/ μ L) groups
- Absolute change from baseline to Week 54 in pre-bronchodilator FEV₁ (liters) within each of the eosinophil-high (≥ 300 cells/ μ L) and eosinophil-low (< 300 cells/ μ L) groups
- Incidence of asthma exacerbations from baseline through Week 54 by *IL1RL1* genotype
- Absolute change in pre-bronchodilator FEV₁ (liters) from baseline to Week 54 by *IL1RL1* genotype

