4.5.3 Exploratory Efficacy Endpoints

Asthma Exacerbation as Defined in Appendix 5

The incidence of asthma exacerbations, defined as in [Appendix 5](#), will be analyzed with the use of the same methodology as described for the primary endpoint (see Section 4.5.1).

Severe Asthma Exacerbations

The incidence of severe asthma exacerbations, defined as asthma symptoms requiring hospitalization or resulting in death attributed to asthma, will be analyzed with the use of the same methodology as described for the primary endpoint (see Section 4.5.1).

Asthma Exacerbations through Week 70

The incidence of severe asthma exacerbations from randomization through Week 70 will be analyzed with the use of the same methodology as described for the primary endpoint (see Section 4.5.1).

Relative Change in Pre-Bronchodilator Forced Expiratory Volume in 1 Second (Liters)

For each patient and timepoint, the relative change in pre-bronchodilator FEV₁ will be defined as the absolute change from the baseline in FEV₁ (liters) divided by the FEV₁ (liters) at baseline. The relative change in pre-bronchodilator FEV₁ from the baseline will be analyzed using the same methodology as described for the secondary endpoint of absolute change in pre-bronchodilator FEV₁ from baseline to Week 54, except that relative change from baseline will be the response variable.

Pre-Bronchodilator Forced Expiratory Volume in 1 Second (Percentage Predicted)

The absolute change in pre-bronchodilator FEV₁ (percentage predicted) from baseline to Week 54 will be analyzed using the same methodology as described for the secondary endpoint of absolute change in pre-bronchodilator FEV₁ from baseline to Week 54.

Pre-Bronchodilator Forced Expiratory Volume in 1 Second (Liters) at Week 70

The absolute change in pre-bronchodilator FEV₁ from baseline to Week 70 will be analyzed using the same methodology as described for the secondary endpoint of absolute change in pre-bronchodilator FEV₁ from baseline to Week 54.

St. George's Respiratory Questionnaire

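### SAP 4.5.3 specifies the Week 70 exacerbation analysis for severe events only, although the listed endpoint is all exacerbations through Week 70, and it leaves the end of time at risk unstated

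*SAP*

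**What the plan says.** SAP 2.1.3 lists the Week 70 endpoint as "Incidence of asthma exacerbations from randomization visit through Week 70". Protocol 6.4.3 lists it as "Incidence of asthma exacerbations from baseline through Week 70", and the protocol synopsis and Table 1 do the same. Severe exacerbations, meaning hospital admission or asthma death, are a separate item in SAP 2.1.3: "Incidence of severe asthma exacerbations from baseline through Week 54".

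SAP 4.5.3 then gives each of these a paragraph. The one on severe exacerbations comes first and refers to Section 4.5.1 for its method. The next is headed Asthma Exacerbations through Week 70, and its only sentence begins: "The incidence of severe asthma exacerbations from randomization through Week 70 will be analyzed with the use of the same methodology". It also refers to Section 4.5.1.

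In Section 4.5.1, time at risk runs from randomization to the actual Week 54 visit for patients who complete the double-blind period. For the others it runs to their last assessment in that period. Only exacerbations with onset inside that time are counted, and the same time is the Poisson offset.

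Two further statements bear on the remedy. Protocol 6.4.3 says: "Analysis of exploratory efficacy endpoints will be described in the SAP". SAP Section 1 says: "No changes to the SAP will be allowed at the time of or subsequent to the 54-week primary analysis".

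**The concern.** The sentence that tells the analyst what to do names a different event from the endpoint it is meant to serve. Followed as written, it produces a comparison of severe exacerbations through Week 70, which neither document lists. The listed comparison of all exacerbations through Week 70 would have no specified analysis.

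Timing gives this some practical weight. The Week 70 data are analysed only after follow-up ends (SAP 2.3), but the SAP may not change from the 54-week analysis onward, when the sponsor's analysis staff are unblinded. If the text is left alone until then, the sponsor must either run the analysis as worded or depart from the SAP after unblinding.

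The second matter is the end of time at risk. The Week 70 sentence names its window but takes its method from a section whose risk period, counting rule and offset all stop at the end of double-blind treatment. The SAP does not say how these extend to Week 70, or where time at risk ends for a patient who leaves during follow-up.

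**Working it through.** The plan gives no figure to reproduce for this analysis. The check is a comparison of the texts, followed by week arithmetic.

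**Event, place by place**

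- SAP 2.1.3, Week 70 item: all asthma exacerbations.
- Protocol synopsis, Table 1 and Section 6.4.3, Week 70 item: all asthma exacerbations.
- SAP 4.5.3, heading of the Week 70 paragraph: all asthma exacerbations.
- SAP 4.5.3, sentence under that heading: severe asthma exacerbations.
- SAP 2.1.3, severe item: through Week 54 only, with its own paragraph in SAP 4.5.3.

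Five places agree and one differs, but the one that differs is the only operative analysis sentence. The word was probably carried over from the paragraph above.

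**Definition once *severe* is deleted**

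The sentence refers to Section 4.5.1, which counts protocol-defined exacerbations under the primary definition. SAP 2.1.1 gives the same definition: "Incidence of asthma exacerbations from baseline through Week 54, with asthma exacerbation defined as new or increased asthma symptoms" and the criteria that follow. Where SAP 2.1.3 means another definition, it says so, as in the Appendix 5 item and the severe item. Items with no stated definition follow the primary one: the eosinophil and *IL1RL1* exacerbation items are analysed in SAP 4.5.6 as the primary endpoint, and time to first exacerbation is analysed in SAP 4.5.2 on protocol-defined events. Deleting *severe* therefore leaves the definition settled by the existing cross-reference.

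**Window, for a patient who completes the study** (randomization at Week 2)

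- Time at risk as defined in Section 4.5.1: 54 − 2 = 52 weeks.
- Time at risk that the Week 70 endpoint needs: 70 − 2 = 68 weeks.
- Difference: 68 − 52 = 16 weeks, which is 16/68 = 23.5% of the 68 weeks.

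The 16 weeks measure how far the two statements differ. They are not a predicted loss, because the sentence itself says through Week 70. The arithmetic does show why the offset must be extended together with the event window. If events were counted to Week 70 over an offset that stopped at Week 54, and the event rate were constant, a completer's annualized rate would be overstated by a factor of 68/52 = 1.31.

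**Size of the event error**

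This would need the proportion of exacerbations that are severe, or a severe-event rate. Neither document gives one. The planning rate of 0.63 per patient per year is for the primary exacerbation endpoint, so it cannot be used for severe events. No figure is claimed.

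**The case against.** The strongest reply is that this is a one-word slip with an obvious intended reading: the heading, the SAP's own endpoint list and the protocol all point the same way. That is right about the cause. It does not remove the need to correct the operative sentence, since an analyst programming from SAP 4.5.3 is told to use severe events.

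A reader might infer more than the documents support in four ways.

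- *The sponsor changed the endpoint to severe events.* Nothing supports this. SAP 2.1.3 and the paragraph heading still give all exacerbations.
- *The SAP overrides the protocol, so the listed endpoint has been replaced.* SAP Section 1 does say: "The analyses specified in this document supersede the high-level analysis plan described in the protocol". That ranks the SAP above the protocol's analysis plan. It does not rank one SAP sentence above SAP 2.1.3 or above its own heading. The conflict lies inside the SAP, and precedence does not resolve it.
- *The last 16 weeks of events will be left out.* The sentence sets its own window through Week 70. The natural meaning of the cross-reference is the same model, covariates and offset approach applied to that window. The same section uses the same shorthand for FEV₁ at Week 70, and no one would take that to stop at Week 54. What remains is an unstated end date.
- *The exacerbation definition would still be open after the correction.* The reference to Section 4.5.1 supplies it.

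**Conclusion.** The inconsistency is real, and the text is wrong as written. The sentence under the Week 70 heading of SAP 4.5.3 analyses severe exacerbations, while the listed exploratory endpoint is all exacerbations through Week 70. Read literally, an unlisted endpoint is analysed and the listed one is not. The secondary point is a gap to fill: the end of time at risk is not stated to match the window.

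The consequence is limited. The effect of the event error cannot be quantified from the documents. The endpoint is exploratory, SAP 4.5 applies no type I error control to it, and no primary or secondary analysis depends on it. The conclusion rests only on the wording of the two documents and needs no assumption about event rates. The point is worth correcting because the correction is very cheap and the SAP sets a deadline for it.

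**What to change.** Before the 54-week analysis, make two edits to the Week 70 exacerbation paragraph of SAP 4.5.3:

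1. Delete *severe*.
2. Add a sentence such as: *For this analysis, time at risk, event inclusion and the offset run from randomization to the Week 70 visit, or to the last study assessment if that is earlier.*

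Keep the reference to Section 4.5.1, which supplies the model, the covariates and the exacerbation definition.

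The cost is one word removed and one sentence added. No new data are needed, because the protocol's schedule of activities already records exacerbations at the Week 62 and Week 70 visits.

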3.3.6 Rationale for Biomarker Assessments

Biomarker assessments, before and at various timepoints after treatment, will be used to demonstrate evidence of the biologic activity of MSTT1041A in patients, identify biomarkers that may be predictive of response to MSTT1041A, define PK/PD relationships, advance the understanding of the mechanism of action of MSTT1041A in patients, support selection of a recommended dose regimen, and increase the knowledge and understanding of disease biology.

Blood samples will be collected at the randomization visit for DNA extraction to enable identification of germline mutations in *IL1RL1*, *IL33*, and *GLCCI1* that may be predictive of response to study drug, are associated with progression to a more severe disease state, or can increase the knowledge and understanding of disease biology.

4. **MATERIALS AND METHODS**

4.1 **PATIENTS**

Approximately 500 patients will be randomized in the study (125 patients in each of the four treatment arms).

4.1.1 **Inclusion Criteria**

4.1.1.1 **Inclusion Criteria for Enrollment in the Run-In Period**

Patients must meet the following criteria to be eligible for enrollment in the run-in period:

- Signed Informed Consent Form
- Age 18–75 years at time of signing Informed Consent Form
- Able to comply with the study protocol, in the investigator's judgment
- Body mass index (BMI) of 18–38 kg/m² and weight ≥ 40 kg at screening
- Documented physician-diagnosed asthma for at least 12 months prior to screening
- On ICS therapy at a total daily dose ≥ 500 µg of fluticasone propionate or equivalent plus at least one additional allowed controller medication, for ≥ 3 months prior to screening, with no changes within 4 weeks prior to screening or during the screening period and no anticipated changes in controller dosing regimens throughout the study

For patients receiving total daily dose of greater than (>) 500 µg of fluticasone propionate or equivalent, they may receive one or more of the following additional controller medications: LABA, LTM, LAMA, or long-acting theophylline preparation.

For patients receiving total daily dose equal to 500 µg of fluticasone propionate or equivalent, at least one of their additional controller medication must be LABA.

- Morning pre-bronchodilator FEV₁ of 40%–80% of predicted at screening
- Post-bronchodilator reversibility of FEV₁ (liters) of ≥ 12% and ≥ 150 mL at screening

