	7. Achievement of improvement Standardized Asthma Quality-of-Life Questionnaires (AQLQS) score, defined as an increase of ≥ 0.5 points from baseline to Week 54			

The testing procedure will be conducted at a two-sided significance level of 5%. Each hypothesis will be formally tested only if the preceding one is significant at 5% level.

No control of type I error will be applied for the exploratory endpoints, including sensitivity, subgroup, and biomarker analyses. Efficacy analyses will not involve formal comparisons between the three MSTT1041A treatment arms (70, 210, and 490 mg).

Covariate Adjustment

Unless otherwise noted, analyses of efficacy endpoints (primary, secondary, and exploratory) will be adjusted for each of the following covariates:

- Blood eosinophil level at visit 1 ($< 150, \geq 150$ to $< 300, \geq 300$ cells/ μ L)
- Number of asthma exacerbations requiring use of systemic corticosteroids within the 12 months prior to study entry (1–2, ≥ 3 events)
- Total daily ICS dose at visit 1 ($< 1000\mu\text{g}, \geq 1000 \mu\text{g}$ of fluticasone propionate or equivalent)
- Geographic region (North America [United States, Canada], Latin America [Argentina, Mexico, Peru], Central and Eastern Europe [Bulgaria, Czech Republic, Poland, Romania, Russia, Serbia, Ukraine], Western Europe plus Rest of World [Australia, Belgium, France, Germany, New Zealand, South Africa, South Korea]).

No missing data of these baseline covariates are expected. Stratification data collected in the IxRS system, rather than on the electronic Case Report Forms, will be used.

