Clinician Global Impression of Change

The CGIC is a single-item assessment of the clinician's impression of a patient's change in asthma symptoms since beginning the 52-week double-blind treatment period. Change in asthma symptoms is rated on a 7-point scale ranging from very much worse to very much improved.

CGIC outcomes will be summarized on the basis of the proportion of patients with an outcome at each of the possible levels (i.e., "very much worse" to "very much improved") by treatment arm and timepoint. The proportion of patients with a "very much improved" or "much improved" CGIC score at Week 54 will be compared between each MSTT1041A arm and the placebo arm with the use of a logistic regression model with terms for treatment arm and the baseline covariates as described in Section 4.5. For patients without a Week 54 assessment, the Week 26 assessment will be used. Patients who have missing CGIC scores at both Weeks 26 and 54 will be excluded from analysis.

Biomarker Subgroup Analyses

Details about efficacy analyses by eosinophil and *IL1RL1* genotype subgroups are presented in Section 4.5.6.

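### The 7-level CGIC is modelled between arms only as a top-two-category responder at Week 54; a supportive proportional-odds model would use the full rating and both listed weeks.

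*SAP*

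**What the plan says.** The CGIC is an ordered rating: "Change in asthma symptoms is rated on a 7-point scale ranging from very much worse to very much improved" (SAP 4.5.3). SAP 2.1.3 lists the endpoint as "Clinician's global impression of change (CGIC) in patient's asthma symptoms, as assessed through use of the CGIC, from baseline to Week 26 and Week 54". Protocol 6.4.3 lists the same endpoint and leaves its analysis to the SAP. Neither list contains a responder threshold.

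SAP 4.5.3 then does two things with the rating.

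- **Description:** "CGIC outcomes will be summarized on the basis of the proportion of patients with an outcome at each of the possible levels", by arm and timepoint.
- **Comparison:** patients rated *very much improved* or *much improved* are counted as responders, and the proportion with such a "CGIC score at Week 54 will be compared between each MSTT1041A arm and the placebo arm with the use of a logistic regression model". The model includes treatment arm and the Section 4.5 covariates. A missing Week 54 rating is replaced by the Week 26 rating, and patients missing both are excluded.

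No ordinal or rank analysis is specified, Week 26 has no modelled comparison, and no reason is given for this cut. On the status of the endpoint, SAP 4.5 states: "No control of type I error will be applied for the exploratory endpoints, including sensitivity, subgroup, and biomarker analyses".

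**The concern.** Once the rating is cut between *minimally* and *much improved*, the model cannot tell apart patients on the same side of the cut. A move from *no change* to *minimally improved*, or from *much* to *very much improved*, leaves the modelled comparison unchanged. If treatment shifts the whole distribution in one direction, the cut gives a wider interval and less power than the same ratings could support.

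The CGIC differs here from AQLQ(S), ACQ-5, ACQ-7 and SGRQ. For those, SAP 2.1.2 and 2.1.3 define the endpoint itself as a threshold. For the CGIC, the listed endpoint is the rating at two weeks, and the threshold appears only in the analysis text. What is at stake is the precision of one exploratory comparison. No confirmatory conclusion depends on it.

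**Working it through.** **No plan figure to reproduce.** The documents give no CGIC distribution, effect size or power. The stated 80% power concerns the exacerbation rate and does not bear on this point.

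**Inputs from the documents**

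- Patients: "Approximately 500 patients will be randomized in the study (125 patients in each of the four treatment arms" (Protocol 4.1); the SAP reports 502 randomized.
- Dropout: 15% (SAP 2.2), so 125 × 0.85 ≈ 106 rated patients per arm. The Week 26 fallback puts the true number between 106 and 125.
- Two-sided 0.05, stated in SAP 4.5 for the primary and secondary endpoints and assumed here for the CGIC.

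**Assumed inputs (not in the documents)**

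- Placebo percentages from best to worst category: A 5/15/35/33/8/3/1, B 10/25/30/25/6/3/1, C 15/35/25/18/4/2/1. The top-two shares are 20%, 35% and 50%.
- One common odds ratio (OR) across all cuts; no covariates.

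**Formulas.** n is the number per arm, m_j the arm-averaged category proportions, and P the arm-averaged top-two proportion.

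- Ordinal information: I_ord = n(1 − Σm_j³)/6
- Information of the cut: I_cut = nP(1 − P)/2
- Ratio: I_cut/I_ord = 3P(1 − P)/(1 − Σm_j³)
- Power ≈ Φ(ln(OR)·√I − 1.96)

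**Worked case: distribution B, OR 1.8, n = 106**

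1. Placebo top-two odds are 0.35/0.65 = 0.538. Times 1.8 gives 0.969, so the active share is 0.492 and P = 0.421.
2. I_cut = 106 × 0.421 × 0.579/2 = 12.9. Power = Φ(0.588 × 3.59 − 1.96) = Φ(0.15) = 56%.
3. Σm_j³ = 0.060, so I_ord = 106 × 0.940/6 = 16.6. Power = Φ(0.588 × 4.08 − 1.96) = Φ(0.44) = 67%.
4. Ratio = 12.9/16.6 = 0.78.

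**All cases at n = 106 (power of cut vs ordinal; information ratio)**

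| Placebo top-two share | OR 1.5 | OR 1.8 | OR 2.2 |
|---|---|---|---|
| 20% (A) | 24% vs 37%; 0.59 | 46% vs 66%; 0.62 | 73% vs 89%; 0.65 |
| 35% (B) | 30% vs 38%; 0.76 | 56% vs 67%; 0.78 | 81% vs 90%; 0.79 |
| 50% (C) | 31% vs 37%; 0.80 | 56% vs 66%; 0.79 | 80% vs 89%; 0.78 |

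At OR 1 the ratios are 0.52, 0.73 and 0.80. The power gap runs from about 6 to 20 points. Simulation (4,000 trials per case; Wald test of the log odds ratio for the cut, Wilcoxon test for the full scale) agrees within about 2 to 3 points, and both tests hold about 5% under the null. With n = 125 and OR 1.8 the formulas give 53% vs 73%, 63% vs 74% and 63% vs 73%, so the Week 26 fallback does not remove the gap.

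**Cases without a common odds ratio (same simulation, n = 106; order A, B, C)**

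| Shift in the active arm | Cut | Full scale |
|---|---|---|
| 15 points from *minimally* to *much improved* | 70%, 58%, 59% | 17%, 19%, 22% |
| 15 points from *no change* to *minimally improved* | about 5% | 28%, 19%, 14% |
| All three *worse* levels to *no change* | about 5% | 11%, 7%, 6% |

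The first row reverses the ordering. The last row shows that the full scale gains little even if every worsening is removed, because the assumed distributions place only 12%, 10% and 7% of placebo patients there.

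**Outside the assumed range.** At the null, the information lost is about 17% for a peaked distribution with a 50% share and about 69% to 72% for a 10% share.

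**The case against.** The strongest reply is that the responder analysis is valid and prespecified, with its model, covariates and missing-data rule. The verbal anchor, at least *much improved*, can be read without an important-difference value, and the responder form matches the other questionnaires. Protocol 6.4.3 leaves the analysis to the SAP, so choosing a cut there contradicts nothing. The CGIC is exploratory, with no power claim, no success criterion and no place in the testing hierarchy. Assuming a common odds ratio also favours the ordinal test. All of this stands. It means the responder model should not be replaced and that this is not an error.

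Three stronger readings are tempting, and the documents do not support them.

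- *The cut discards a fixed share of the information.* The share depends on a distribution and an effect pattern that the documents do not give.
- *The plan ignores the lower categories.* SAP 4.5.3 tabulates every level by arm and timepoint. Only the modelled comparison omits shifts that stay on one side of the cut.
- *An ordinal model would reveal a drug that prevents worsening.* Under the assumed distributions it has 6% to 11% power even if all worsening disappears. Worsening is also measured by the exacerbation endpoints.

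The reply leaves two facts in place: the model uses one cut of a seven-level rating, and one of the two listed weeks has no modelled comparison.

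**Conclusion.** The point holds as an inexpensive improvement. The only modelled CGIC comparison is the top two categories against the other five at Week 54. If a common odds ratio of 1.5 to 2.2 applies, with about 106 patients per arm and a placebo top-two share of 20% to 50%, the cut gives up about 6 to 20 points of power and retains about 59% to 80% of the ordinal information (52% at the null with a 20% share). All the CGIC inputs are assumptions and the figures are illustrations, not bounds. If the effect is concentrated at the cut, the planned test is clearly the better one. Each analysis covers a case in which the other is weak, which is the reason to report both.

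**What to change.** In SAP 4.5.3, keep the top-two logistic regression as written and add a supportive analysis:

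- a proportional-odds logistic regression on the full CGIC scale, each dose against placebo, at Week 54 (with the same Week 26 substitution) and at Week 26;
- the same treatment terms and Section 4.5 covariates;
- the common odds ratio with its 95% CI;
- a pooling rule fixed in advance, for example merging the three *worse* levels. At an assumed 1%, the worst level holds about one patient per arm. Under distribution B, pooling raises Σp_j³ from 0.0595 to 0.0603, a loss of about 0.1% of the information.

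The cost is one paragraph and one further exploratory model on data already collected, with no effect on alpha. The downside is the proportional-odds assumption, which the planned category table lets readers check. SAP Section 1 bars changes at or after the 54-week primary analysis, so the addition must be made before then; otherwise it should be labelled post hoc.
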